6.6.3 Lactation

Whether SHR-1210 is secreted in breast milk is unknown. Considering that many drugs are present in breast milk, SHR-1210 may be potentially toxic to infants. Thus, lactating women who are breast feeding must not be enrolled in this study.

6.7 Subject Compliance

The medication compliance of the subject undergoing study treatment at the study center will be monitored through the following visits:

- Tablets: Subjects will be required to return all unused study drugs from the previous cycle before the commencement of the next cycle. The number of tablets returned by the subjects will be counted, recorded, and archived.
- Drugs for intravenous infusion: The study center shall prepare the drugs and complete the documentation as per the product brochure or package insert of the study drugs. The documentation system of the study center should include all relevant or required information with regards to preparation and administration.

6.8 Return and Disposal of Drugs

In this study, the containers, vials, infusion bags, and syringes of study drugs that are used and partially used may be destroyed on-site according to the guidelines and operating procedures established by the study center and local institutions.

All unused study drugs shall be returned to the sponsor for destruction after the study is completed/terminated or after the expiry date. The return of the study drugs will be arranged by the clinical research associate designated by the sponsor.

6.9 Handling of Complaints

To ensure the safety of subjects and the quality of monitoring, and to assist in the improvement of processes and drugs, the sponsor will collect product complaints related to the study drugs used in the clinical study.

Complaints related to concomitant medications will be reported directly to the manufacturer according to the product information.

The investigator or designated person thereof is responsible for completing the following product complaint procedures in accordance with the relevant requirements of this study:

- Use a study-specific complaint form to record the reported product complaints and relevant complete descriptions.
- Fax the completed product complaint form to the sponsor or designated person thereof within 24 hours.

If the investigator is required to return the product for investigation, the investigator should return a copy of the product complaint form together with the product.

7 STUDY PROCEDURES

7.1 Procedures of Subject Enrollment and Randomization

7.1.1 Subject enrollment

The investigator will enroll the subjects following the steps below:

1. Obtain an ICF with the subject's signature before proceeding with any study-related procedures.
2. The principal investigator or designated person thereof with appropriate training will formally determine the eligibility of the subject after reviewing the inclusion/exclusion criteria.

The sponsor will monitor the enrollment of each cohort such that the sample size of each cohort meets the study requirements.

Subjects who do not meet the relevant criteria of this study (screening failure) may be rescreened. If re-screening of subjects is considered, the investigator must contact the sponsor's medical department. Each subject may be re-screened once. For rescreening, the subject must re-sign the ICF and will be assigned another subject ID.

In the first stage, if the subject develops PD, withdraws the ICF, develops intolerance without completing the 28-day observation before withdrawal, or does not meet the inclusion/exclusion criteria, the principal investigator of the leading center and the sponsor may decide whether to enroll additional subjects as appropriate.

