10 DATA ANALYSIS/STATISTICAL METHODS

10.1 Sample Size

In this study, based on historical study data and study results of drugs of the same class and combined with clinical needs, a single-stage assessment method will be adopted to explore the efficacy of SHR-1210 combined with apatinib on ORR in ED-SCLC after failure of the first-line standard therapy.

Assume that in this study, the expected ORR in each treatment group of SHR-1210 + apatinib combination therapy is $\geq 30\%$ (alternative hypothesis), and that there is no need to continue the study if the ORR is $\leq 15\%$ (null hypothesis), at the significance level of 0.1 and a power of 80%, 40 subjects should be enrolled. If ≥ 9 (22.5%) of the 40 subjects have response, it can be considered that the ORR in this treatment group is 15% and the study drug is worthy of continued development.

With a dropout rate of 10% taken into account, each treatment group needs to enroll about 45 subjects. A total of 57 subjects are required in Stages I and II.

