10.3 Statistical Hypotheses

This study does not involve any statistical hypotheses and inference.

A single-stage assessment method will be adopted to explore the efficacy of SHR-1210 combined with apatinib on ORR in ED-SCLC after failure of the first-line standard therapy. The potential need for further development is indicated when the predefined number of responses (objective response) of a treatment group is reached (see Section 10.1 for details).

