5 STATISTICAL ANALYSIS

5.1 General Considerations

5.1.1 Analysis sets

The analysis sets in this study included:

Full analysis set (FAS): an analysis set determined based on the intent-to-treat principle. This analysis set includes all enrolled subjects who have received at least one dose of the study drug. Based on the FAS, the subjects will be analyzed according to their scheduled doses.

Per-protocol set (PPS): a subset of the FAS. Subjects with major protocol violations that have a major effect on the study results will be excluded from this set. The list of subjects included into or excluded from the PPS should be reviewed and determined by the sponsor and the investigator before the database is locked.

Safety set (SS): all subjects who have received at least one dose of the study drug and underwent post-administration safety evaluation. Analyses based on the safety set will be carried out according to the actual treatment received by the subjects.

ADA set (ADAS): All enrolled subjects who have received at least one dose of the study drug and have baseline and at least one post-baseline ADA evaluation data.

Tumor biomarkers set (TMKS): all enrolled subjects who have received at least one dose of the study drug and have tumor biopsy samples (including peripheral blood) make up the PD-L1 or TMB set.

Table X. Analysis sets and corresponding endpoints

Endpoint	Analysis Sets				
	FAS	PPS	SS	ADAS	TMKS
Safety Endpoints	X				
ORR	X	X			
OS and 6/12-month OS rates	X				
PFS	X				
TTR	X				
DoR	X				
DCR	X				
Immunogenicity Evaluation				X	
Tumor Biomarkers					X

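### Stage I subjects may be added after an early PD while the go rule stays a fixed count of responses, which slightly raises the false-go rate as written (minor)

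*Protocol*

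**What the plan says.** **Adding subjects.** Protocol 7.1.1 gives four grounds: "In the first stage, if the subject develops PD, withdraws the ICF, develops intolerance without completing the 28-day observation before withdrawal, or does not meet" (eligibility being the fourth ground). In those cases "the principal investigator of the leading center and the sponsor may decide whether to enroll additional subjects as appropriate". There is no cap, and nothing says how the original or the added subject counts for ORR. The study is open-label (Protocol 7.1.3) and has no central imaging review (Protocol 8.1).

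**Who counts for ORR.** The FAS is the primary ORR set (Protocol 10.5.2; SAP 5.4.1). SAP 5.1.1: "This analysis set includes all enrolled subjects who have received at least one dose of the study drug". Protocol 10.4 also keeps everyone randomized and dosed. SAP 4.1 ends best overall response at PD, so PD before any response is a non-response.

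**The go rule.** Protocol 10.3: "The potential need for further development is indicated when the predefined number of responses (objective response) of a treatment group is reached". Protocol 10.1 sets the number at 9 or more of 40, printed with 22.5% beside it. The null ORR is 15%, the alternative is 30%, and "at the significance level of 0.1 and a power of 80%, 40 subjects should be enrolled". Allowing 10% dropout gives about 45 per group.

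**Totals.** Protocol section 4 plans 6 subjects per group in Stage I and 39 in Stage II. Protocol 10.1: "A total of 57 subjects are required in Stages I and II".

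**The concern.** PD before any response is a failure on the primary efficacy endpoint. If that failure lets two parties who can see it enroll one more subject, and the required number of responses does not change, the number of chances to reach 9 depends on the outcome. The original subject stays in the FAS as a non-responder, but under a count rule a non-responder costs nothing, and the added subject can only help. The shift is always towards go. Only additions in the group taken into Stage II matter, and only six subjects are planned there in Stage I.

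**Working it through.** **1. The plan's own rule.** Exact binomial tails, P(X ≥ r) for X ~ Bin(n, p):

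| Rule | False go at ORR 15% | Go at ORR 30% |
|---|---|---|
| 9 of 40 (as printed) | 0.135 | 0.889 |
| 10 of 40 | 0.067 | 0.804 |
| 9 of 45 | 0.225 | 0.953 |
| 11 of 45 | 0.065 | 0.835 |

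The printed cut-off of 9 does not reproduce a significance level of 0.1; at n = 40 a cut-off of 10 meets both 0.1 and 80%. The sizes do reproduce: 40/0.9 = 44.4, rounded up to 45; 6 + 39 = 45; 18 + 39 = 57. That Stage I subjects count towards the go decision is inferred from 6 + 39 = 45.

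**2. Model for additions.** Let q be the chance that a Stage I subject has PD that triggers an addition. It is not in the documents; the range used is 0.02 to 0.30. The 39 Stage II subjects follow Bin(39, p). For the six Stage I places:

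- *One round of additions:* a place yields a response if its first subject responds (probability p), or if that subject has early PD and the added one responds (q × p). Total: p(1 + q).
- *Additions until six complete 28 days:* p/(1 − q) per place.

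At p = 0.15 and q = 0.10 these are 0.165 and 0.1667. Combining Bin(6, ·) with Bin(39, 0.15):

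| q | Expected additions | False go, count 9 | Rise (points) | False go, count 11 |
|---|---|---|---|---|
| 0 | 0 | 0.2255 | – | 0.0651 |
| 0.02 | 0.12 | 0.228 | +0.2 | 0.066 |
| 0.05 | 0.3 | 0.231–0.232 | +0.6 | 0.068 |
| 0.10 | 0.6–0.7 | 0.237–0.239 | +1.2 to +1.3 | 0.070–0.071 |
| 0.20 | 1.2–1.5 | 0.249–0.256 | +2.4 to +3.0 | 0.076–0.079 |
| 0.30 | 1.8–2.6 | 0.262–0.278 | +3.6 to +5.2 | 0.082–0.089 |

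Cross-check: with the count fixed at 9, the false-go rate is 0.2255 at N = 45 and 0.2457 at N = 46, about 2 points per added subject. At q = 0.02, 0.12 × 2 ≈ 0.24 points, as in the table.

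**3. Which q is plausible.** The first scheduled post-baseline scan is C1D28 (Protocol 8.1.2), with a ±3-day window in note 20 to the Schedule of Activities. If the 28-day limit in 7.1.1 covers PD as well as intolerance, PD must be seen clinically, on an unscheduled scan, or on a scan taken on days 25 to 27. That points to the low rows. The wording does not settle whether the limit covers PD, so the higher rows are kept as an outer range.

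**4. If the group is held at 45.** If one fewer Stage II subject is enrolled for each addition and the PD subject stays in the FAS, the total is Bin(45, 0.15) and the false-go rate stays at 0.2255.

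**5. Scaling the cut-off.** The smallest count with exact false-go rate at or below 0.10 is 11 for N = 45 to 48 (0.065, 0.075, 0.085, 0.096) and 12 for N = 49 to 51 (0.055, 0.063, 0.071).

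**The case against.** The clause looks like a safety provision. It keeps enough subjects for the 28-day assessment, which SAP section 6 limits to adverse event and laboratory listings with no efficacy analysis. PD is one of four grounds. Protocol 7.1.1 also has the sponsor monitor each cohort's enrollment so that its size meets requirements, which could mean the group is held at 45, and then nothing is inflated. The 45 already includes a 10% allowance over 40. The 22.5% beside the 9 might be read as a proportion.

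Much of this stands. It does not close the gap, because no sentence limits added subjects to safety, Stage II is a flat 39, and Protocol 10.3 and SAP section 3 word the rule as a number of responses. Both also say that no hypotheses are involved, yet the same sections make that number the development signal.

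Stronger readings are not supported:

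- *The false-go rate is left without control because of 7.1.1.* Most of the excess over 0.1 is in the cut-off: 13.5% at 40 and 22.5% at 45 before anyone is added. With a count of 11, every modelled case stays below 0.10.
- *A rise of several points is to be expected.* That needs q of about 0.2 to 0.3, which the documents do not give and the scan schedule makes unlikely if the 28-day limit covers PD.
- *The ORR estimate is inflated.* Under the FAS the PD subject stays in the denominator. The weakness is in the unscaled count.
- *Subjects would be added to gain responses.* Nothing in the documents suggests this.

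**Conclusion.** The point holds as a minor one. Following the written FAS and count rules literally, an addition after early PD in the group chosen for Stage II moves the false-go rate upwards only. The rise is about 0.2 to 1.3 points on 22.5% for q of 0.02 to 0.10, and up to 5.2 points at q = 0.30. This rests on three assumptions: Stage I subjects count towards the go decision, the 39 Stage II subjects are enrolled in full on top of any additions, and q lies in the stated range. The first two are readings of the text; the third is not in the documents. The calculation covers additions for PD only. The cut-off of 9 is the larger problem, and correcting it would also absorb this one.

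**What to change.** State in Protocol 7.1.1 and 10.3, and in SAP sections 3 and 5.4.1, that a dosed Stage I subject with early PD stays in the ORR analysis as a non-responder. Then choose one of these in advance:

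1. **Fixed population.** The go decision uses the first six dosed subjects in the selected group plus the 39 Stage II subjects (N = 45). Added subjects count for the Stage I safety review and the safety tables. ORR in the full FAS, including them, is also reported.
2. **Scaled cut-off.** All FAS subjects count, and the cut-off follows the actual FAS size: at least 11 for N = 45 to 48, at least 12 for N = 49 to 51. This keeps the false-go rate below 0.10 and discards nobody.

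Either takes about one sentence in each document and needs no extra patients or procedures. Under option 1, the go decision and the full-FAS ORR use slightly different populations. The go probability at ORR 30% is lower than if added subjects counted, by about 0.1 to 2 points with a count of 9 and 0.3 to 5.5 points with a count of 11. Option 1 alone leaves the false-go rate at 22.5% if the count stays at 9. Option 2 lowers the go probability at ORR 30% from 0.953 to 0.835 at N = 45, which is the price of meeting 0.1 and is still above the planned 80%.

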7.1.2 Handling procedures for mistakenly enrolled subjects

The inclusion/exclusion criteria must be strictly followed. In the case where subjects who do not meet the inclusion/exclusion criteria are enrolled, the sponsor's medical department and the investigator shall discuss and determine whether to allow the subjects to continue to participate in the study, i.e., whether or not to administer the study drugs. If the investigator believes that it is medically appropriate for the subject to continue participating in the study, and the sponsor's medical department agrees with the investigator's decision, the subject may continue participating in the study and undergo the study treatment. If the investigator believes that it is medically appropriate for the subject to continue participating in the study, but the sponsor's medical department does not agree with the investigator's decision, the subject shall not continue participating in the study (whether or not to undergo the study treatment). Only after the investigator receives written approval from the sponsor can the subjects who are unqualified for the inclusion/exclusion criteria be enrolled for continued participation in the study.

7.1.3 Randomization and blinding

This study is open-label and does not involve blinding. Eligible subjects after screening will be randomized into the following three treatment groups in a 1:1:1 ratio: SHR-1210 200 mg, IV, Q2W + apatinib 375 mg, PO, QD; SHR-1210 200 mg, IV, Q2W + apatinib 375 mg, PO, QD (5 Days on, 2 Days off); or SHR-1210 200 mg, IV, Q2W + apatinib 375 mg, PO, QD (7 Days on, 7 Days off).

7.2 Main Study Procedures

7.2.1 Screening period (visit 1)

Refer to [Table 11](#) for procedures of visits during the screening period.

Table 11. Procedures of visits during the screening period

Period	Screening Period			Note
Day	-28 to -1	-7 to -1	-3 to -1	
Baseline				
ICF	X			Subjects who do not meet the relevant criteria of this study (screening failure) may be rescreened. See Section 7.1.1 of the protocol for rescreening procedures

Period	Screening Period			Note
	Day	-28 to -1	-7 to -1	
Inclusion/Exclusion Criteria	X			
Demographics/Medical History/Medication History	X			The medications include treatment for initial diagnosis, including chemotherapy, radiotherapy, and surgical treatment. The time of the last anti-tumor treatment must be recorded.
Vital Signs	X			Vital signs include body temperature, pulse, respiratory rate, and blood pressure. See Section 8.2.4 of the protocol for detailed requirements
Weight/Height	X			
Physical Examination	X			See Section 8.2.2 of the protocol
ECOG PS	X			
Laboratory tests				
12-Lead ECG	X			Refer to Section 8.2.3 of the protocol for details
Hematology/Clinical Chemistry/Urinalysis/Routine Stool		X		See Section 8.2.1 of the protocol
Coagulation Function		X		
Pregnancy Test			X	Serum pregnancy test
Thyroid Function	X			See Section 8.2.7 of the protocol
Myocardial Zymogram		X		See Section 8.2.7 of the protocol
Pituitary Adrenal Axis Test	X			Applicable to hospitals where conditions permit
HIV, HBV, and HCV	X			See Section 8.2.7 of the protocol
Echocardiography	X			See Section 8.2.7 of the protocol
Pulmonary function test and arterial blood gases	X			See Section 8.2.7 of the protocol
AE Assessment	X			All AEs from the time of signing the ICF to the end of safety follow-up or the start of new anti-tumor therapy (whichever occurs first) and all SAEs from signing of ICF to the end of safety follow-up will be recorded in the CRF
Concomitant Medications	X			Drugs related to the treatment of AEs other than solvents within 28 days before the first dose of the study drug until 30 days after and 30 to 60 days after the end of the treatment should be documented
Response Evaluation				

Period	Screening Period			Note
	Day	-28 to -1	-7 to -1	
Imaging Assessment	X			See Section 8.1 of the protocol
Exploration of Biomarkers				
Archived or Fresh Tumor Tissue Sample	X			5-10 unstained tissue slices with thickness of 4-6 μ m
Peripheral Blood	X			Collect 16 mL of peripheral blood for tumor biomarker detection

7.2.2 Treatment period (visits 2 to N)

Refer to [Table 12](#) for procedures of visits during the treatment period.

Table 12. Procedures of visits during the treatment period

Period	Treatment Period				Note
	Cycle 1		Cycle 2 and thereafter		
Day	1	15 (\pm 3 days)	1 (\pm 3 days)	15 (\pm 3 days)	
Vital Signs	X	X	X	X	Vital signs include body temperature, pulse, respiratory rate, and blood pressure. Before each SHR-1210 administration. See Section 8.2.4 of the protocol for detailed requirements
Body Weight	X	X	X	X	Before each SHR-1210 administration
Physical Examination		X	X	X	Before each SHR-1210 administration. See Section 8.2.2 of the protocol
ECOG PS	X	X	X	X	Before each SHR-1210 administration
Laboratory Tests					
12-Lead ECG	X	X	X	X	After each SHR-1210 infusion. See Section 8.2.3 of the protocol for detailed requirements
Hematology/Clinical Chemistry/Urinalysis/Routine Stool		X	X	X	Before each SHR-1210 administration. See Section 8.2.1 of the protocol
Coagulation Function			X		Before each SHR-1210 administration
Thyroid Function	X		X		Before each SHR-1210 administration
Myocardial Zymogram					Performed when clinically indicated per the investigator's judgment

Period	Treatment Period				Note		
	Cycle 1		Cycle 2 and thereafter				
Day	1	15 (± 3 days)	1 (± 3 days)	15 (± 3 days)			
Pituitary Adrenal Axis Test			X		Applicable to hospitals where conditions permit; before each SHR-1210 administration		
Echocardiography					Performed when clinically indicated per the investigator's judgment		
Pulmonary function test and arterial blood gases					Performed when clinically indicated per the investigator's judgment		
Immunogenicity (ADA, Nab)	X		X		Sampling will be performed once within 0.5 h prior to SHR-1210 infusion on D1 of Cycle 1, Cycle 2, and every 3 cycles thereafter (Cycles 5, 8, 11, and so forth). If the subject develops SHR-1210-related infusion reactions, blood samples should be collected as close as possible to the onset of the event, to the end of the event, and about 30 days after the end of the event, for immunogenicity comparison and analysis. Tests will be performed at the central laboratory		
AE Assessment	X		X		All AEs from the signing of the ICF to the end of safety follow-up or the start of a new anti-tumor treatment (whichever comes first) and all SAEs from the signing of the ICF to the end of safety follow-up should be recorded in the CRF		
Concomitant Medications	X		X		Drugs related to the treatment of AEs other than solvents within 28 days before the first dose of the study drug until 30 days after and 30 to 60 days after the end of the treatment should be documented		
Response Evaluation							
Imaging Assessment	X		X		See Section 8.1 of the protocol		
Infusion of Study Drugs							
SHR-1210	IV, Q2W				See Section 6.1.1 of the protocol for the administration regimen. Subjects who meet specific conditions may continue the medication after PD (refer to Section 6.1.2 of the protocol for continued medication beyond progression).		

Period	Treatment Period				Note
	Cycle 1		Cycle 2 and thereafter		
Day	1	15 (± 3 days)	1 (± 3 days)	15 (± 3 days)	
Apatinib	PO				See Section 6.1.1 of the protocol for the administration regimen.
Exploration of Biomarkers					
Peripheral Blood	X				Collect approximately 16 mL of peripheral blood for tumor biomarker detection during each tumor evaluation period

7.2.3 End of treatment

End of treatment refers to confirmation of progressive disease or withdrawal from the study. The end-of-treatment visit should be performed within ±3 days of the decision of treatment discontinuation and/or withdrawal from the study (refer to Table 13).

Table 13. Procedures of the end-of-treatment visit

Period	End of treatment	Note 28 Days (± 7 Days)
Day	± 3 days	
Vital Signs	X	Vital signs include body temperature, pulse, respiratory rate, and blood pressure. See Section 8.2.4 of the protocol for detailed requirements
Body Weight	X	
Physical Examination	X	See Section 8.2.2 of the protocol
ECOG PS	X	
Laboratory tests		
12-Lead ECG	X	Refer to Section 8.2.3 of the protocol for details
Hematology/Clinical Chemistry/Urinalysis/Routine Stool	X	See Section 8.2.1 of the protocol
Coagulation Function	X	
Pregnancy Test		Serum pregnancy test
Thyroid Function	X	
Myocardial Zymogram	X	
Pituitary Adrenal Axis Test	X	Applicable to hospitals where conditions permit
Echocardiography	X	
Pulmonary function test and arterial blood gases		Performed when clinically indicated per the investigator's judgment
Immunogenicity (ADA, Nab)	X	

Period	End of treatment	Note 28 Days (± 7 Days)
Day	± 3 days	
AE Assessment	X	All AEs from the time of signing the ICF to the end of safety follow-up or the start of new anti-tumor therapy (whichever occurs first) and all SAEs from signing of ICF to the end of safety follow-up will be recorded in the CRF
Concomitant Medications	X	Drugs related to the treatment of AEs other than solvents within 28 days before the first dose of the study drug until 30 days after and 30 to 60 days after the end of the treatment should be documented
Response Evaluation		
Imaging Assessment	X	See Section 8.1 of the protocol
Exploration of Biomarkers		
Archived or Fresh Tumor Tissue Sample	X	5-10 unstained tissue slices with the thickness of 4-6 µm, among which at least 5 slices will be used for PDL1 testing
Peripheral Blood	X	16 mL of peripheral blood will be collected for tumor biomarker detection

